3.1.4 Rationale for Dose Selection

In the Blinded Part A of this study, the 2 dose levels of mRNA-1273 tested in participants will be 50 µg and 100 µg, based on assessment of available safety and immunogenicity data from the Phase 1 DMID study and Phase 1 studies of mRNA-1647 and mRNA-1443 (Section 1).

The Phase 1 DMID study, an open-label dose-ranging study of mRNA-1273 in healthy adult male and non-pregnant female participants in 3 age groups: age 18 to 55 years, inclusive (45 participants); age 56 to 70 years, inclusive (30 participants); and \geq 71 years (30 participants) is currently ongoing. Participants in each age cohort will be randomly assigned to 1 of 3 dose levels of mRNA-1273: 25 µg, 100 µg, and 250 µg. Each participant will receive an IM injection (0.5 mL) of mRNA-1273 on Days 1 and 29 in the deltoid muscle and will be followed for 12 months after the second injection.

As of 14 May 2020, 15 participants in each of the 3 dose levels of the 18 to 55-year age cohort received at least 1 dose of mRNA-1273. Recruitment of participants in the 2 older age cohorts is ongoing. There have been no SAEs and no triggering of study pause rules. A review of preliminary solicited local and systemic ARs in participants in the 18 to 55-year age cohort after the second injection showed 3 participants in the 100 µg dose group who reported severe local ARs (Grade 3 erythema and induration) and 3 participants in the 250 µg dose group who reported severe systemic ARs (fever, fatigue, feverishness, myalgia, and nausea). These ARs resolved within 24 hours and were not assessed as serious.

The 50 µg and 100 µg doses proposed for this Phase 2a study fall within the doses being evaluated in the Phase 1 DMID study. Specifically, in Part B of the amended study, the decision to provide a booster dose to those participants who received two doses of 50 or 100 µg is, in part, to address the waning neutralizing antibody titers seen in the Phase 1 DMID study beginning 4 months after the first vaccination (Widge et al 2021). Furthermore, the choice of a 50 µg dose level as a booster is supported by data from Phase 2 studies indicating that the immune response is largely indistinguishable between 50 and 100 µg.

In Part C of the amended study, participants will receive a single booster dose of either mRNA-1273.351 (20 µg or 50 µg) or mRNA-1273/mRNA-1273.351 mixture (50 µg total; 25 µg of mRNA-1273 and 25 µg of mRNA-1273.351). The dose ranging will help assess the potential for cross-priming by the variant vaccine. In addition, the inclusion of the choice of the 20-µg dose level as a booster is intended to help assess the stability of the 50 µg dose of the vaccine at the limits of the anticipated expiration.

3.1.5 Rationale for Study Design

The 2 age cohorts in this Phase 2a study, ≥ 18 to < 55 years old and ≥ 55 years old, were established to better understand the relationships among dose, tolerability, and immunogenicity in different age groups, one being healthy older adults. The older cohort in this Phase 2a study corresponds to the 2 older age cohorts in the Phase 1 DMID study.

Because there are currently no licensed SARS-CoV-2 vaccines available, 0.9% sodium chloride will be used as a placebo control for the safety and immunogenicity assessments. Consequently, the mRNA-1273 vaccine and placebo injections will look different, so administration will be blinded in Part A of the study ([Section 3.3.5](#)).

The Phase 1 DMID study is small (105 participants at 3 dose levels) and does not incorporate a placebo. Having a sample size of 600 participants in this Phase 2a study and including a placebo will help to improve understanding of AEs.

With SARS-CoV-2 expected to be circulating in the general population during the study, all participants will provide pre-injection blood samples and post-injection blood samples for antibody analysis through 12 months after the last dose of investigational product. In addition, participants will have nasopharyngeal swab samples collected at Day 1 and Day 29, before the injections, and at Day 57. Furthermore, with any signs or symptoms or MAAE suggesting SARS-CoV-2 infection in a participant, an additional nasopharyngeal swab sample and a blood sample will be taken to confirm the diagnosis of SARS-CoV-2 via serology and polymerase chain reaction (PCR). Additionally, clinical information will be carefully collected to evaluate the severity of the clinical case.

Since it is possible that participants are naturally exposed to SARS-CoV-2 through community exposure, the nasopharyngeal swab samples collected before study injection may help discriminate between natural infection and vaccine-induced antibody responses, should such discrimination be needed.

Following authorization of a COVID-19 vaccine under EUA, this study amendment is designed to transition to Part B, the Open-Label Interventional Phase ([Figure 3](#)). Transitioning the study to Part B, Open-Label Interventional Phase, permits all ongoing study participants to (a) be informed of the availability and eligibility criteria of any COVID-19 vaccine made available under an EUA and (b) the option to offer all ongoing study participants who request unblinding an opportunity to schedule a study visit to know their original group assignment (placebo vs. mRNA-1273 [50 μ g or 100 μ g vaccine]). Part B, Open-Label Interventional Phase, also provides the opportunity for study participants who previously received placebo to request to receive 2 doses of mRNA-1273 (100 μ g) vaccine. Participants who originally received mRNA-1273

(50 µg or 100 µg vaccine) will have the opportunity to request to receive a single booster dose of mRNA-1273 (50 µg).

As SARS-CoV-2 variants with mutations in the S protein have emerged, we are learning about the clinical significance to ongoing global vaccination efforts based on strains derived from the Wuhan virus. A variant first identified in South Africa (B.1.351) is associated with increased transmission, higher viral burden, and possibly increased mortality in infected persons ([Tegally et al 2020](#)). The development and testing of vaccines targeting this SARS-CoV-2 variant is urgently needed.

mRNA-1273.351, like mRNA-1273, encodes the prefusion stabilized S protein of SARS-CoV-2. However, the mRNA of mRNA-1273.351 incorporates the key mutations present in the B.1.351 strain of the virus. Part C of this study will evaluate the immunological benefit of boosting participants previously vaccinated with mRNA-1273 (mRNA-1273-P301 COVE study) with the B.1.351 strain-specific S protein (mRNA-1273.351) and the mRNA-1273/mRNA-1273.351 mixture, which incorporates 25 µg of each of the Wuhan -1 and B.1.315 representative sequences, for a total dose of 50 µg.

Healthy male or female participants will be enrolled at study sites in the US or its territories.

3.1.6 Inclusion Criteria

Each participant must meet all of the following criteria during the screening period and at Day 1/OL-D1, unless noted otherwise, to be enrolled in this study:

Male or female, 18 years of age or older at the time of consent (Screening Visit, Day 0). For **Part B**, participants must have been previously enrolled in the mRNA-1273 P201 study. For **Part C**, participants must have been previously enrolled in the mRNA-1273-P301 COVE study, must have received two doses of mRNA-1273 in Part A of that study (ie, already unblinded and aware of their actual treatment), with their second dose at least 6 months prior to enrollment in this part, and must be currently enrolled and compliant in that study (ie, not have withdrawn or discontinued early).

Understands and agrees to comply with the study procedures and provides written informed consent.

According to the assessment of the investigator, is in good general health and can comply with study procedures.

3.1.6.1 Inclusion criterion specific for Parts A and B:

1. Female participants of nonchildbearing potential may be enrolled in the study. Nonchildbearing potential is defined as surgically sterile (history of bilateral tubal ligation, bilateral oophorectomy, hysterectomy) or postmenopausal (defined as amenorrhea for ≥ 12 consecutive months prior to Screening (Day 0) without an alternative medical cause). A follicle-stimulating hormone (FSH) level may be measured at the discretion of the investigator to confirm postmenopausal status.
2. Female participants of childbearing potential may be enrolled in the study if the participant fulfills all the following criteria:
 - Has a negative pregnancy test at Screening (Day 0) and on the day of the first injection (Day 1).
 - Has practiced adequate contraception or has abstained from all activities that could result in pregnancy for at least 28 days prior to the first injection (Day 1).
 - Has agreed to continue adequate contraception through 3 months following the second injection (Day 29).
 - Is not currently breastfeeding.

Adequate female contraception is defined as consistent and correct use of a Food and Drug Administration (FDA) approved contraceptive method in accordance with the product label. For example:

- Barrier method (such as condoms, diaphragm, or cervical cap) used in conjunction with spermicide
- Intrauterine device
- Prescription hormonal contraceptive taken or administered via oral (pill), transdermal (patch), subdermal, or IM route
- Sterilization of a female participant's monogamous male partner prior to entry into the study

Note: periodic abstinence (eg, calendar, ovulation, symptothermal, post-ovulation methods) and withdrawal are not acceptable methods of contraception.

3. Male participants engaging in activity that could result in pregnancy of sexual partners must agree to practice adequate contraception and refrain from sperm donation from the time of the first injection and through 3 months after the last injection.

Adequate contraception for male participants is defined as:

- Monogamous relationship with a female partner using an intrauterine device or hormonal contraception (described above)
- Use of barrier methods and spermicide
- History of surgical sterilization
- Male participants with partners who have become pregnant prior to Screening are eligible to participate in the study.

3.1.6.2 Inclusion criterion specific for Part C:

1. Female participants of nonchildbearing potential may be enrolled in the study. Nonchildbearing potential is defined as surgically sterile (history of bilateral tubal ligation, bilateral oophorectomy, hysterectomy) or postmenopausal (defined as amenorrhea for ≥ 12 consecutive months prior to Screening (Day 0) without an alternative medical cause). The FSH level may be measured at the discretion of the investigator to confirm postmenopausal status.
2. Female participants of childbearing potential may be enrolled in the study if the participant fulfills all the following criteria:
 - Has a negative pregnancy test at Part C OL-Day 1 and on the day of injection.
 - Has practiced adequate contraception or has abstained from all activities that could result in pregnancy for at least 28 days prior to the injection (OL-Day 1).
 - Has agreed to continue adequate contraception through 3 months following the second injection (OL-Day 57), as applicable.
 - Is not currently breastfeeding.
3. Adequate female contraception is defined as consistent and correct use of a Food and Drug Administration (FDA) approved contraceptive method in accordance with the product label. For example:
 - Barrier method (such as condoms, diaphragm, or cervical cap) used in conjunction with spermicide
 - Intrauterine device

- Prescription hormonal contraceptive taken or administered via oral (pill), transdermal (patch), subdermal, or IM route
- Sterilization of a female participant's monogamous male partner prior to entry into the study
- Note: periodic abstinence (eg, calendar, ovulation, symptothermal, post-ovulation methods) and withdrawal are not acceptable methods of contraception.

4. Adequate contraception for male participants is defined as:

- Monogamous relationship with a female partner using an intrauterine device or hormonal contraception (described above)
- Use of barrier methods and spermicide
- History of surgical sterilization
- Male participants with partners who have become pregnant prior to Screening are eligible to participate in the study.

5. Healthy adults or adults with pre-existing medical conditions who are in stable condition. A stable medical condition is defined as disease not requiring significant change in therapy or hospitalization for worsening disease during the 3 months before enrollment.
6. For Part C, participants must have provided SARS-CoV 2 serology samples at Day 1, Day 29, Day 57, and at the Participant Decision Visit (OL-D1) in Moderna's COVE study.

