The placebo is 0.9% sodium chloride (normal saline) injection, United States Pharmacopeia (USP).

Investigational product will be administered as an IM injection into the deltoid muscle on a 2-dose injection schedule on Day 1 and Day 29 in Part A and on Open Label (OL) Days 1 and 29 in Part B

(for participants receiving 2 doses of mRNA-1273), with a 28-day interval between doses. Participants receiving a single booster dose of mRNA-1273 in Part B will receive their dose on OL-D1. Each injection will have a volume of 0.5 mL and contain mRNA-1273 50 µg, mRNA-1273 100 µg, or saline placebo. Upon consent to roll over, participants in Part C will receive a single booster dose of mRNA-1273.351 (20 µg or 50 µg) or mRNA-1273/mRNA-1273.351 mixture (50 µg total). Preferably, the vaccine should be administered into the nondominant arm.

Unblinded pharmacy personnel, who will not participate in any other aspect of the study during Part A, the Blinded Phase, will perform vaccine accountability, dose preparation, and vaccine administration. In Part B, study site personnel who were blinded during the Blinded Phase, will be unblinded at the Participant Decision Visit.

Part B and C of the study will be open label.

Sample Size:

There is no hypothesis testing in this study. The number of proposed participants is considered sufficient to provide a descriptive summary of the safety and immunogenicity of different dose levels of mRNA-1273.

In the blinded Part A, approximately 600 participants will be randomly assigned in a 1:1:1 ratio to mRNA-1273 50 µg, mRNA-1273 100 µg, or placebo. A total of 400 participants will receive mRNA-1273, 200 participants in each dose level, or 100 participants in each age cohort and dose level. A sample size of 400 has at least a 95% probability to observe at least 1 participant with an AE at a true 0.75% AE rate. Participants who received any injection in Part A will have the opportunity to enter Part B provided that they meet the eligibility criteria.

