3.4.4 Safety Laboratory Assessments

In the blinded Part A of the study, laboratory tests will be performed by the central laboratory unless otherwise specified. Screening safety laboratory tests will include complete blood count with differential, alanine aminotransferase (ALT), aspartate aminotransferase (AST), total and direct bilirubin, alkaline phosphatase (ALP), blood urea nitrogen/creatinine, prothrombin time (PT), and partial thromboplastin time (PTT). These safety laboratory tests are to be repeated at Day 29 and Day 57 only for Cohort 2 (≥ 55 years of age).

Additional tests include the following:

In both Parts A and B, a point-of-care urine pregnancy test will be performed at the Screening Visit (Day 0) or Participant Decision Visit (OL-Day 1) and before each vaccine administration. In Part C, a point-of-care urine pregnancy test will be performed at the OL-Day 1 prior to vaccine administration.

At any time, a pregnancy test either via blood or point-of-care urine can be performed, at the discretion of the investigator.

- If not documented in a female participant's medical records, an FSH test may be performed at the Screening Visit (Day 0, Part A, Blinded Phase only), as necessary and at the discretion of the investigator, to confirm postmenopausal status.
- Hepatitis B surface antigen, hepatitis C virus antibody, and HIV virus (types 1 and 2) antibody at the Screening Visit (Day 0, Part A, Blinded Phase only).

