3.4.9 Vital Sign Measurements

Vital sign measurements will include systolic and diastolic blood pressure, heart rate, respiratory rate, and body temperature (preferred route is oral). The participant will be seated for at least 5 minutes before all measurements are taken. Vital signs will be measured at the time points indicated in the Schedule of Events ([Table 9](#), [Table 11](#), and [Table 12](#)). In all parts, blinded and open label, on Day 1 and Day 29 (as applicable), vital sign measurements will be collected once before vaccine administration and at least 30 minutes (Part A) and 30 minutes (Parts B and C) after vaccine administration (before participants are discharged from the study site).

Febrile participants at Day 1 and Day 29 (Parts A, B, and C) visits (fever is defined as a body temperature $\geq 38.0^{\circ}\text{C}/100.4^{\circ}\text{F}$) may be rescheduled within the relevant window periods. Afebrile participants with minor illnesses may be injected at the discretion of the investigator.

When procedures overlap and are scheduled to occur at the same time point, the order of procedures should be vital sign measurements and then the blood collection.

If any of the vital sign measurements meet the toxicity grading criteria for clinical abnormalities ([Table 13](#)) of Grade 3 or greater, the abnormal value and grade will be documented on the AE page of the eCRF (unless there is another known cause of the abnormality that would result in an AE classification). The investigator will continue to monitor the participant with additional assessments until the vital sign value has reached the reference range, returns to the vital sign value at baseline, is considered stable, or until the investigator determines that follow-up is no longer medically necessary.

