3. Physical examination: A symptom-directed physical examination, including height and weight, will be performed at OL-Day 1, OL-Day 29, and OL-Day 57. Symptom-directed physical examinations may be performed at other time points at the discretion of the investigator. Any clinically significant finding identified during a study visit should be reported as an MAAE. Vital signs are to be collected pre- and post-dosing on days of injection (Day 1 and Day 29). When applicable, vital sign measurements should be performed before blood collection. Participants who are febrile (body temperature $\geq 38.0^{\circ}\text{C}/100.4^{\circ}\text{F}$) before injection on OL-Day 1 or OL-Day 29 must be rescheduled within the relevant window period to receive the injection. Afebrile participants with minor illnesses can be administered investigational product at the discretion of the investigator.
4. Sample must be collected prior to dosing on days of injection.
5. The nasopharyngeal swab sample, collected prior to vaccination on days of injection, will be used to ascertain the presence of SARS-CoV-2 via PCR.
6. Diary entries will be recorded by the participant starting approximately 30 minutes after injection while at the study site with instruction provided by study staff. Study participants will continue to record in the eDiary each day after they leave the study site, preferably in the evening and at the same time each day, on the day of injection and for 6 days following injection. Any solicited AR that is ongoing beyond Day 7 will be reported in the eDiary until resolution. Adverse reactions recorded in eDiaries beyond Day 7 should be reviewed either during the next telephone call or at the next study site visit.

7. Trained site personnel will call all participants to collect information relating to any AEs, MAAEs, SAEs, AEs leading to study withdrawal, information on concomitant medications associated with those events, and any non-study vaccinations. In addition, study personnel will collect information on known participant exposure to someone with known COVID-19 or SARS-CoV-2 infection and on participant experience of COVID-19 symptoms. Sites will collect this information for diary days only if diary responses indicate the need for follow-up via telephone.

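### The female contraception rule for Parts A and B ends 3 months after a Day 29 second injection, so it does not cover the 3 months after a single Part B booster; the male rule does.

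*Protocol*

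**What the plan says.** Section 3.1.6.1 applies to both Part A and Part B. The opening clause of Section 3.1.6 requires the criteria to be met "during the screening period and at Day 1/OL-D1, unless noted otherwise, to be enrolled in this study". Table 12, the booster schedule, has eligibility confirmed at OL-D1, and Section 4.5 makes entry to Part B conditional on eligibility.

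- **Women, lead-in:** contraception or abstinence "for at least 28 days prior to the first injection (Day 1").
- **Women, end of period:** "Has agreed to continue adequate contraception through 3 months following the second injection (Day 29").
- **Men, whole period:** "from the time of the first injection and through 3 months after the last injection".

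On the regimen, the Synopsis (investigational product and dosage) states: "Participants receiving a single booster dose of mRNA-1273 in Part B will receive their dose on OL-D1". Section 3.3.2 agrees. Section 3.1.2 notes that a participant with two Part A doses who takes the booster has three injections in all.

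**The concern.** The female end point is tied to a numbered dose on a named day. That worked in Part A, where the second injection was the last one planned. It does not suit the booster, which has no second Part B injection. A woman who meets the criterion again at OL-D1 is renewing a commitment that runs from an earlier dose.

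Followed as written, her required contraception can end before the booster or shortly after it, while a man given the same dose is bound for 3 months. What is at stake is protection against pregnancy in the period after a study vaccine dose. No endpoint, sample size or estimate is affected.

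**Working it through.** The plan gives no figure for this point. The check sets the rule against each Part B group and then against the calendar.

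**Which injection the rule points to**

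| Woman entering Part B | Part B doses | Second injection on a Day 29 | Does the rule reach 3 months past her last dose? |
|---|---|---|---|
| Placebo in Part A, takes mRNA-1273 | OL-Day 1 and OL-Day 29 | OL-Day 29, if Day 29 is read that way | Yes, on that reading |
| Two mRNA-1273 doses in Part A, takes booster | OL-Day 1 only | Part A Day 29, in the past | No |
| One mRNA-1273 dose in Part A, takes booster | OL-Day 1 only | None | Unclear: the booster is her second injection, but not on Day 29 |

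The reading in the first row is fair, because the protocol uses these day labels loosely for open-label visits. Section 3.4.9 says "In all parts, blinded and open label, on Day 1 and Day 29 (as applicable"), and Table 11 footnote 3, which concerns Part B only, says "Vital signs are to be collected pre- and post-dosing on days of injection (Day 1 and Day 29"). Reading Day 1 as OL-D1 for the 28-day lead-in is fair for the same reason.

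**Inputs for the calendar check**

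- Second Part A doses reported as of 05 Nov 2020 (Section 1.3): 195 in the 50 µg group and 198 in the 100 µg group, out of 200 each.
- Amendment 4, which added Part B, is dated 15 Jan 2021 (Section 7.3.2). Assumption: no booster before that date.
- The current protocol is dated 28 Apr 2021 (page header; SAP Section 1).

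**Participants by number of Part A doses, both sexes**

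- Two doses: 195 + 198 = 393 of 400 (98%).
- One dose: 400 − 393 = 7.

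**Latest end of female cover:** 05 Nov 2020 + 3 months = 05 Feb 2021.

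**Days uncovered = days in the 3 months after the booster − days from the booster to 05 Feb 2021 (zero if that date has been reached)**

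| Booster date | Booster + 3 months | Days in period | Covered | Uncovered |
|---|---|---|---|---|
| 15 Jan 2021 | 15 Apr 2021 | 90 | 21 | 90 − 21 = 69 |
| 05 Feb 2021 | 05 May 2021 | 89 | 0 | 89 |
| 28 Apr 2021 | 28 Jul 2021 | 91 | 0 | 91 |

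In the last row cover had already lapsed for 82 days when the booster was given (05 Feb to 28 Apr 2021). An earlier Part A second dose or a later booster widens the gap, so 69 days is a minimum under the stated assumptions.

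**Other safeguards.** Section 3.4.4 requires a pregnancy test at "Participant Decision Visit (OL-Day 1) and before each vaccine administration" and allows one at any time at the investigator's discretion. Section 3.3.2.2 makes pregnancy a bar to further doses, and Section 3.4.8.5 covers reporting and follow-up. None of these sets a contraception period. Table 12 schedules pregnancy testing only at OL-D1.

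**The case against.** Five points can be made on the other side.

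1. **The consent form may settle it.** Every participant signs a revised form at the Participant Decision Visit. The Amendment 1 history shows that this trial's form deals with the subject: the male criterion was changed then to match it. This stands as a limit. What can be shown is a fault in the protocol, not that women were left without any commitment. A longer commitment in the form would still leave the criterion wrong.
2. **The difference between the sexes looks like leftover wording.** In Part A the second and last injections were the same dose for anyone who completed the schedule. That is probably how it arose, but the text still governs Part B.
3. **A site could read Day 29 as the OL-Day 29 visit, which booster participants do attend.** Three months from that visit would exceed 3 months from the booster. But the rule counts from an injection, and booster women have none that day.
4. **Few women are exposed.** By Table 1, half of the planned mRNA-1273 recipients are in the cohort aged 55 or older, so the relevant group lies mainly among about 200 younger recipients of both sexes. It narrows further to women of childbearing potential who accept a booster. This stands, and it limits the scale.
5. **The absence of a later scheduled pregnancy test is not particular to the booster.** Part A schedules none after its last dose either. This also stands, so the missing test is background and the case does not rest on it.

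**Conclusion.** The concern holds. For a woman who had two Part A doses, the criterion sets no contraception period running to 3 months after the Part B booster, and no other section of the reviewed documents sets one. For a woman with one Part A dose the text is ambiguous. For crossover women there is a gap only if Day 29 is not read as OL-Day 29.

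Under the assumed dates (Part A second dose by 05 Nov 2020, booster from 15 Jan 2021), between 69 of 90 days and the whole 3 months after the booster are uncovered. Actual booster dates and the number of women of childbearing potential are not in the documents. The fault is in a participant-protection rule and should be corrected; it has no bearing on the statistical analysis.

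**What to change.** In Section 3.1.6.1, end the female commitment *3 months after the last injection (Part A or Part B)*, in line with the male rule. For clarity, also state the 28-day lead-in as *prior to Day 1 or OL-D1*; this second change is helpful but not essential.

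The cost is about one line of protocol text, carried into the consent form if it is not already there. Visits, data collection and analyses are unchanged.
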